9.3 Subject Enrolment and Informed Consent

Patients presenting to their physician in need of assessment or removal of peripheral pulmonary nodule(s), and who meet study inclusion/exclusion criteria, will be invited to participate. Patient enrolment will follow each participating institution's standard of care. Subjects will be approached to obtain informed consent prior to any study-specific procedure. Informed consent will take place in a private environment (e.g. patient exam room), free from distractions. The PI or study team member will approach the subject at their clinic appointment and will explain the study to qualified subjects prior to obtaining consent. All individuals who obtain consent (PI, Sub-investigators, and study coordinators) must have received GCP informed consent training within the past 2 years. Interviews to obtain consent will not follow any stressful situation (e.g. patient being informed he/she may have cancer) and will not be conducted if the patient has received any mind-altering medications or anesthesia. Patients will be assessed for their capacity to consent by the ability to show comprehension of the procedure, ask appropriate questions, and appear properly oriented.

The PI will confirm subject eligibility. Patients who sign the informed consent form will be considered enrolled. A signed copy of all consents and the HIPAA authorization document will also be given to consenting subjects.

Patients who complete the localization procedure will be included within the analysis population. Reasons for study withdrawal will be recorded. Each patient's participation in this study is approximately 6 weeks baseline through subject's discharge from hospital following lung surgery.

9.4 Withdrawal of Subjects

Following informed consent, subjects withdrawn from the study prior to the localization procedure due to patient withdrawal of consent or at the discretion of the investigator will be considered withdrawn. In the case of investigator withdrawal, the reason for early withdrawal will be documented. Data collected from all treated patients undergoing localization will be included within the analysis population.

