DIAGNOSIS AND MAIN CRITERIA FOR INCLUSION	
Subjects will be eligible to enroll into the registry if they have given their informed consent and also meet the following criteria:
 
Inclusion criteria:
 
• Subject's physician and/or thoracic surgeon have deemed/has deemed that the surgical removal of the PPN is appropriate.• A clinical decision has been made to use the SPiN Thoracic Navigation System™.• Subject is at least 18 years of age at time of study entry.• Subject is able to read, understand, and voluntarily sign the IRB-approved informed consent document prior to the performance of any study-specific procedures. IRB-approved translation may be used if indicated. Reasonable accommodation of visually impaired subjects will be allowed.• Subject is able to tolerate general anesthesia.• Subject has a target nodule between 0.4 cm and 3.2 cm in greatest dimension;• The target nodule is in a location that is accessible for percutaneous localization in the judgement of the surgeon. 
Exclusion criteria:
 
• Subjects with any other concomitant treatment or medical condition that, in the opinion of the clinician, would render peripheral nodule resection more hazardous than beneficial.• Subject is pregnant.• Pulmonary nodule is greater than 3.2 cm.• Subjects with significant coagulopathy having INR >2.0 or PTT > 2x normal.• Subject is unable to tolerate general anesthesia• Obese subject, impacting percutaneous access (BMI >50)
TEST PRODUCT AND MODE OF ADMINISTRATION	
Localization of nodules will be completed with the SPiN Thoracic Navigation System™, and the corresponding tools that allow for percutaneous access. These include the SPiN Perc™ Kit and the 1 cm and 2 cm Localization Needles. Please refer to protocol section 5, and also the IFU and product information (Appendix A). Investigators are trained in the use of the tools and the system.

REFERENCE THERAPY	Historical data as available.
DURATION OF SUBJECT INVOLVEMENT	Duration of treatment studied during the registry will be up to approximately 6 weeks per subject, including screening and baseline visits, surgery, and hospital visit.
SAFETY ASSESSMENTS	Localization-related events will be collected.

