3. RATIONALE

Veran Medical Technologies, Inc. is seeking to characterize the efficient localization and successful removal of PPNs aided by the technique of percutaneous localization within the operating room. This falls within the current practice for these subjects. However, the characterization and comparison of various localization techniques has not been reported prospectively in a large, multicenter approach.

To realize this opportunity, further localization methodologies must be developed. Percutaneous nodule localization involves various factors. Nodular size and location (near the pleura) can both introduce challenges for unequivocal localization and complete removal. PPNs can be difficult to locate and access in order to mark them. It can be difficult to find the marked nodules, depending upon the location and how well the localization technique worked during the resection surgery. This registry will collect data regarding different techniques used by thoracic surgeons using a choice of localization materials (dye, hookwire etc.) and with electromagnetic navigation guidance using a transthoracic approach. Evidence from a multicenter, prospective registry trial on localization procedures will allow us to understand the best practices in the localization of PPNs that also minimizes risks in subjects who are typically older, have comorbid lung disease, poor pre-surgical lung function and may have early stage lung cancer.

[figure not shown]
Further, the study will allow us to describe the use of VERAN SPiN Thoracic Navigation System™ and percutaneous lung localization tools in a real-world thoracic surgery practice, including duration of localization procedure, duration of the resection procedure, and other data elements.

TABLE 1 – SCHEDULE OF EVENTS

Procedures/Data Collection	Baseline Visit	Day 0 Surgery Localization Procedure
Nodule is correct size and suitable for percutaneous localization during surgical resection procedure.	X	X
Subject meets Inclusion/Exclusion criteria review.	X	
Subject is able and willing, and signs consent form.	X	
Pregnancy test- urine or serum, for females of child-bearing potential.	X	X
Socio-demographic information.	X	
Pulmonary function test results	X	
Brief Medical History, including previous cancer diagnoses, smoking, and treatment history.	X	
Nodule hx, dx, characteristics if known.	X	
Recent (0-15 days) CT scan available, or schedule CT scan to be used on day of surgery, prior to procedure.	X	X

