If the nodule is fully removed in crossover cases, then the primary endpoint is met. The nodule may be removed per the surgeon's judgement. The pathology findings will then identify the entire case as either benign or malignant, and the primary endpoint is met.

If Diagnosis is Non-malignant

If the nodule is deemed non-malignant, cells are identifiable, then the positive box for diagnosis is checked, and:

- The nodule must have an intact margin of a cell as a perimeter to be diagnostic.
- The type of nodule (ground glass opacity, etc.) is collected from the pathology report.

The pathology findings will then identify the case as either benign or malignant.

9.3 Safety Objective:

Record Safety Events During Intraoperative Percutaneous Localization Only

To collect and evaluate the safety of nodule localization, including incidence and severity of localization-procedure related adverse events (AEs) and serious adverse events (SAEs) that occur during the localization procedure.

Baseline/Enrollment

All patients will be provided with information about the registry and will sign the informed consent form before any registry-related assessments are made. The following data will be collected at baseline for all enrolled patients:

- To be collected at baseline visit: Review of inclusion/exclusion criteria.

Localization Period

- The localization period begins when the needle touches the subject's skin.
- Localization ends when the localization needle is withdrawn from the subject for the final time.
- Any adverse events that develop during the localization procedure will be reported.
- Bronchoscopy-related events that occur during the alignment of the CT with the patient ("registration") will be recorded.
- Percutaneous localization step, injection of dye, injection of any microcoils, etc.

The process used for AE reporting conforms to Veran Medical Technologies, Inc., standard operating procedures (SOPs) for Medical Device Reporting (MDR)(Appendix C). Training on AE/SAE/MDR reporting practices will be provided to each participating site.

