9.5 Screen Failures

Subjects who provide informed consent but are determined to be ineligible prior to the index procedure will be considered screen failures. The reason for screen failure will be documented. The assigned subject ID for the subject will not be re-used.

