9.9 Nodule Localization

The bronchoscope (Olympus MP-160 or BF-190) will be introduced into the airway. A Veran tip tracked instrument will then be introduced into the working channel of the bronchoscope and utilizing standard Veran System navigation-matching protocols, the main and secondary carinas are identified using the tip tracked instrument to confirm that the Veran System is properly matched to the airway defined by accurate matching of the main and secondary carina. This allows the system to align the CT with the patient's current position.

Following registration, a sterile field is created on the chest wall as identified by the Spin Perc planning software and the area is prepped and draped. A tip tracked needle, such as one of the Veran localization needles or the Veran tip tracked Spin Perc needle introducer, is selected. The surgeon advances the needle trans thoracically into the nodule, under Veran EMN guidance, to the nodule. The nodule is localized percutaneously by marking with dye using an assortment of tools designed for this purpose (Section 5.1), adding microcoils or fiducials, etc.

Data Collected: patient position, registration, volume of dye, type of dye, use of microcoils or fiducials.

The surgeon then continues to wedge resection, and the registry portion of the procedure is completed.

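### The primary denominator is not tied to a defined start of localization, so failed or abandoned SPiN attempts can drop out of the success rate and bias it upward

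*Combined protocol and SAP*

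**What the plan says.** **Denominator.** Section 4.1 divides by evaluable subjects and defines them as those who *complete* localization. Section 9.3 (Subject Enrolment and Informed Consent) uses the same verb for the analysis population. Section 9.4 instead includes treated patients *undergoing* localization, and section 11.1 those who *undergo* it and meet the entry criteria.

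**Withdrawal.** Section 9.4 covers subjects "withdrawn from the study prior to the localization procedure due to patient withdrawal of consent or at the discretion of the investigator". It gives no criteria for that discretion. For investigator withdrawals, "the reason for early withdrawal will be documented".

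**Start of localization.** The Localization Period list under the 9.3 Safety Objective says "The localization period begins when the needle touches" the skin. The same list also records bronchoscopy events during registration. Section 9.9, headed Nodule Localization, begins earlier: the bronchoscope goes in and a tip-tracked instrument is used "to confirm that the Veran System is properly matched to the airway defined by accurate matching of the main and secondary carina". Only then is the chest prepared and a needle chosen.

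**Screen failure.** Section 9.5 reads: "Subjects who provide informed consent but are determined to be ineligible prior to the index procedure will be considered screen failures". The term index procedure is not defined. One inclusion criterion rests on the surgeon's opinion: "The target nodule is in a location that is accessible for percutaneous localization in the judgement of the surgeon". Table 1 marks this item at both Baseline and Day 0: "Nodule is correct size and suitable for percutaneous localization during surgical resection procedure". It marks the inclusion/exclusion review at Baseline only.

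**Scoring.** No section says how a failed registration or an abandoned attempt is scored.

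**The concern.** Section 4.1 sets out to measure the accuracy of localization with the SPiN system and its accessories. Use of that system begins at registration. If the CT cannot be matched to the airway, or no usable path is found, and the surgeon proceeds to resection without marking the nodule, the system has not delivered what is being measured. Under most readings of the text that subject is not in the denominator.

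Three features make this matter. The Background states the aim of keeping localization and resection in the principal investigator's hands, so the person exercising the 9.4 discretion can be the unblinded operator. There is no comparator arm in which the same selection would show. And section 11.1 targets 70-100 *evaluable* patients, so excluded subjects can be replaced and the final number need not reveal the loss. The reported rate could then describe mainly cases in which navigation had already worked.

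**Working it through.** **Step 1. Which subjects count under each reading.** Two start points and two verbs give four combinations.

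| Start of procedure | Verb | Failed registration or no usable path | Needle attempt abandoned |
|---|---|---|---|
| Needle to skin (9.3 Safety Objective) | complete | out | out* |
| Needle to skin | undergo | out | in |
| Bronchoscope introduced (9.9) | complete | out | out* |
| Bronchoscope introduced | undergo | in | in |

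*Unless final withdrawal of the needle, which the safety text gives as the end of localization, is itself taken as completion.

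Pre-needle failures are out in three of the four readings, without any withdrawal decision. The completer wording is therefore the main cause, and the 9.4 discretion is a second route. Choosing *undergo* throughout brings these subjects back only if the start is also fixed at registration.

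**Step 2. Size.** The plan has no figure to reproduce: section 11.1 states that no formal sample size estimation was used, and no expected rate is given. The inputs are:
- n = 70 or 100 evaluable subjects (section 11.1);
- x = successes among them, near 80%, 90% or 95% (assumed);
- k = subjects started but lost before the needle, about 5% or 10% of n + k (assumed).

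If the k subjects are scored as failures, the excess is x/n − x/(n+k) = (x/n) × k/(n+k).

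| n | x/n | k about 5% | Rate | Excess, points | k about 10% | Rate | Excess, points |
|---|---|---|---|---|---|---|---|
| 70 | 56/70 = 80.0% | 4 | 75.7% | 4.3 | 8 | 71.8% | 8.2 |
| 70 | 63/70 = 90.0% | 4 | 85.1% | 4.9 | 8 | 80.8% | 9.2 |
| 70 | 66/70 = 94.3% | 4 | 89.2% | 5.1 | 8 | 84.6% | 9.7 |
| 100 | 80/100 = 80.0% | 5 | 76.2% | 3.8 | 11 | 72.1% | 7.9 |
| 100 | 90/100 = 90.0% | 5 | 85.7% | 4.3 | 11 | 81.1% | 8.9 |
| 100 | 95/100 = 95.0% | 5 | 90.5% | 4.5 | 11 | 85.6% | 9.4 |

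The range is about 4-5 points at 5% and 8-10 points at 10%. At a 2% share it is about 1-2 points. With k = 0 it is zero.

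For scale, the Clopper-Pearson 95% interval for 90/100 is 82.4-95.1%. The rate on all started cases with k = 11 is 81.1%, below that interval.

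**Step 3. Dependence on scoring.** Sections 4.1 and 9.2 say that a specimen with clear margins counts as a successful localization. If all 8 excluded subjects at n = 70 were kept and scored as successes on that ground, 63/70 = 90.0% would become (63+8)/(70+8) = 71/78 = 91.0%. The direction therefore depends on a scoring rule that the plan does not state for these cases.

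**The case against.** A reader might infer that sections 9.4 and 9.5 expressly let the surgeon remove a subject up to needle contact after registration has failed, and that the rate is therefore inflated, always upward. The documents do not support this.

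- Neither section mentions registration or the needle. The needle cut-off comes from the safety text. If section 9.9 describes the localization procedure, the 9.4 exit already closes when the bronchoscope is introduced.
- Section 9.5 is a rule on ineligibility. Failure to match the CT to the airway does not make a nodule's location inaccessible. At most, a path found unusable could be relabelled as inaccessibility.
- Upward bias requires that such exits occur and that they would score as failures. Step 3 shows that the clear-margin sentence could be read the other way. The reply is that the endpoint also requires the nodule to be localized, which an unmarked nodule is not; but the plan should say so.

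There are also partial safeguards. Reasons for investigator withdrawal and for screen failure are documented, and section 6.3 requires device deficiencies, including use error, to be reported. The study is descriptive, and section 11.2.1 defers detail to a written analysis plan. These records make pre-needle failures traceable, but no rule brings them into, or beside, the primary rate.

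Finally, a rate conditional on localization having taken place is a legitimate quantity, and counting every stopped case as a failure would charge the device with stops for anaesthetic or other unrelated reasons. Both points stand. They are reasons to keep the completer rate as supportive and to separate non-device stops.

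**Conclusion.** The concern holds as an unsettled denominator with a risk of upward bias; inflation is not demonstrated. The main source is the completer definition in 4.1 and 9.3 (enrolment). It conflicts with 9.4 and 11.1, and the start of localization is undefined. The uncriteriated discretion in 9.4 adds selection by the operator. Attempts abandoned after needle contact are exposed under the completer wording as well as pre-needle failures.

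The excess is about 4-10 percentage points if 5-10% of started cases are lost before the needle and score as failures, for 70-100 evaluable subjects and completer rates of roughly 80-95%. The loss shares and success rates are assumptions. With no exits there is no effect.

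**What to change.** 1. Define the start of the localization procedure once, as introduction of the bronchoscope or tip-tracked instrument for SPiN registration, and use that definition throughout.
2. In 9.4, state that from that point withdrawal at the investigator's discretion does not remove a subject from the analysis. The patient's right to withdraw consent is unaffected.
3. In 4.1, 9.3 (enrolment) and 11.1, make the primary denominator all eligible subjects in whom registration was started. Take eligibility as recorded before that point, so that a path later found unusable is not recoded as ineligibility.
4. Score attempts with no percutaneous localization achieved (failed registration, no usable path, abandoned needle attempt) as failures, even if the later specimen has clear margins.
5. Tabulate stops for non-device reasons separately, and give a sensitivity rate that excludes them.
6. Report the completer rate as supportive, with a flow of consented, withdrawn, screen-failed, registration started, needle placed and completed, with reasons.

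The cost is protocol wording and one eCRF field (registration started / matched / needle placed); section 9.9 already lists registration among the data collected. No procedures are added. The headline rate may be a few points lower.

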9.5 Screen Failures

Subjects who provide informed consent but are determined to be ineligible prior to the index procedure will be considered screen failures. The reason for screen failure will be documented. The assigned subject ID for the subject will not be re-used.

9.6 Pre-procedure Chest CT Scan Evaluation

After informed consent is obtained, the patient's most recent chest CT scan or chest x-ray will be deidentified and securely downloaded and saved. If subjects have multiple pulmonary nodules, the site PI will identify the target nodule.

9.7 Non-contrast Chest CT

It is recommended by the manufacturer that the subject receives a non-contrast chest CT scan be performed on the same day as the procedure as a clinically indicated procedural planning tool (Veran Appendix B – technical description of CT parameters). Otherwise, a chest CT scan from within the past 15 days may also be used when it is consistent with these parameters.

9.8 General Anesthesia

Patients will undergo the procedure under general anesthesia.

9.9 Nodule Localization

The bronchoscope (Olympus MP-160 or BF-190) will be introduced into the airway. A Veran tip tracked instrument will then be introduced into the working channel of the bronchoscope and utilizing standard Veran System navigation-matching protocols, the main and secondary carinas are identified using the tip tracked instrument to confirm that the Veran System is properly matched to the airway defined by accurate matching of the main and secondary carina. This allows the system to align the CT with the patient's current position.

Following registration, a sterile field is created on the chest wall as identified by the Spin Perc planning software and the area is prepped and draped. A tip tracked needle, such as one of the Veran localization needles or the Veran tip tracked Spin Perc needle introducer, is selected. The surgeon advances the needle trans thoracically into the nodule, under Veran EMN guidance, to the nodule. The nodule is localized percutaneously by marking with dye using an assortment of tools designed for this purpose (Section 5.1), adding microcoils or fiducials, etc.

Data Collected: patient position, registration, volume of dye, type of dye, use of microcoils or fiducials.

The surgeon then continues to wedge resection, and the registry portion of the procedure is completed.

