OBJECTIVES	
The registry is aimed developing a high-quality set of data regarding intraoperative percutaneous localization of peripheral pulmonary nodules (PPNs), and then identifying and promulgating efficient, evidence-based best practices for this technique. The resection procedure itself is standard of care and follows the investigator's standard protocol.
 
Successful localization of PPNs is a challenge involving multiple factors, beginning with the subjects' health, lung function and also factors specific to the nodule including location within the lung, size, distance from the lung surface, whether solid or ground glass and proximity to a fissure. Hard to see or palpate nodules are currently localized with dye and/or hook wires or fiducials, either endoscopically or percutaneously. Successful, large, prospective studies have not been reported using modern electro-magnetic navigation (EMN)-guided percutaneous intraoperative localization, and different techniques (dye vs. fiducial vs. hook wire etc.) have not been evaluated. It is for these reasons that the different localization techniques used with EMN-guided percutaneous localization will be collected for patients having a suspicious nodule and who undergo percutaneous intra-operative localization and immediate resection.
 
This registry aims to record the localization techniques used by thoracic surgeons and IP/surgical teams to identify PPNs using the SPiN Thoracic Navigation System™ in the hands of trained physicians. The objectives of this study will be to accomplish the

	primary and secondary objectives listed below, and to observe localization in a real-world context of pulmonary resection.
PRIMARY OBJECTIVE	Successful percutaneous localization of PPN. This is defined as the percentage of subjects in whom the nodule is successfully localized and removed in the first resected specimen. A pathological specimen with clear margins will count as a successful localization.
SAFETY OBJECTIVES	
1. Report the incidence of device-related adverse events that occur during the localization procedure.

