9.2 Primary Efficacy Objective: Successful Percutaneous Localization of PPN

This is defined as the percentage of subjects in whom the nodule is successfully localized and removed in the first resected specimen. A pathological specimen with clear margins will count as a successful localization.

To evaluate the accuracy of percutaneous nodule localization using the SPiN Thoracic Navigation System™ and its accessories, by recording the percentage of successful nodule resections that result in the complete removal of the patient's nodule, with at least a one cell perimeter and negative margins. The diagnostic yield is calculated as the percentage of patients who have intra-operative localizations resulting in complete removal of nodule, divided by the total number of evaluable subjects.

Confirmation of Diagnosis

Surgical pathology results will determine the outcome of the primary endpoint. If the patient has follow-up imaging that shows a decrease in size or resolution of the nodule, the nodule will be determined to be of benign etiology if the study pathology yields a benign diagnosis (granuloma, inflammation, fibrosis, infection). To verify final diagnosis, a copy of the final pathology report will be de-identified and provided by the site. The pathology findings will then identify the case as either benign or malignant. Whether a benign or malignant diagnosis is made, the primary endpoint is met.

If Margins are Intact

If the nodule has intact margins as described by the pathology report. Explicitly, a perimeter of at least one cell around the nodule contain cells that are all non-malignant. This plus the nodule sample verifies that the entire nodule was removed. The pathology findings will then identify the case as either benign or malignant.

Crossover Cases

It is anticipated that there will be cases where the wedge is positive for malignancy and the deep margin also will be positive. In these cases, the surgical plan may change from a planned wedgeectomy into a completion lobectomy or segmentectomy. If the nodule is fully removed

(having at least a cell's margin of non-malignant cells in these cases, then the primary endpoint is met. The pathology findings will then identify the entire case as either benign or malignant, and the primary endpoint is met.

Margins for Crossover Cases

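### Clear margins alone score the primary endpoint, and no described item records whether the SPiN-placed mark guided the first resection, so a rescued mark failure counts as a SPiN success

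*Combined protocol and SAP*

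**What the plan says.** **Endpoint.** Section 4.1 gives the purpose as evaluating the accuracy of SPiN-guided percutaneous localization. On the endpoint, section 9.2 says: "This is defined as the percentage of subjects in whom the nodule is successfully localized and removed in the first resected specimen". The next sentence, which also stands in the synopsis and section 4.1, supplies the scoring rule: "A pathological specimen with clear margins will count as a successful localization". Section 9.2 then names the deciding source: "Surgical pathology results will determine the outcome of the primary endpoint".

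**Data at the localization step.** Section 9.9 has "Data Collected: patient position, registration, volume of dye, type of dye, use of microcoils or fiducials", followed by "The surgeon then continues to wedge resection, and the registry portion of the procedure is completed". Under Localization Period (section 9.3, Safety Objective), "Localization ends when the localization needle is withdrawn from the subject for the final time".

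**Data after that step.** The synopsis and sections 4.3, 9 and 10.3 still provide for resection type and technique, planned and eventual surgery, total surgical duration, excised weight, margin, pathology, and localization adverse events through discharge. Section 9 also says that localization outcomes will be recorded and that procedures assisting surgical management will be noted. Section 10.2 points to Appendix B for the full data elements.

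**Expected mark performance.** Section 3 accepts that a mark may not serve its purpose: "It can be difficult to find the marked nodules, depending upon the location and how well the localization technique worked during the resection surgery".

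**Eligibility.** The size criterion is "Subject has a target nodule between 0.4 cm and 3.2 cm in greatest dimension". No criterion requires the nodule to be hard to see or feel, although the synopsis objectives describe such nodules as the ones currently localized.

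**The concern.** The endpoint definition has two parts, localization and removal, but only removal has a named data source. A pathology report shows that the nodule is in the specimen and that its margins are clear. It cannot show whether the surgeon followed the SPiN-placed mark, felt the nodule, saw it, or used something else.

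The registry has a single arm, with historical data as the only reference, so no comparator separates mark performance from surgical skill. The protocol also wants to characterize and compare localization techniques and to identify best practice. If mark failures are rescued and scored as successes, each technique's rate moves towards 100% and the differences between techniques shrink. The effect would be largest wherever nodules are easiest to find unaided, plausibly the larger or more superficial ones.

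**Working it through.** There is no figure in the plan to reproduce. Section 11.1 states that no formal sample size estimation was used, and no performance target is given. The check is therefore a reading of the data items, followed by an illustration of size.

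**Step 1. Does any described item show how the nodule was found?**

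| Item | Where | Shows how the nodule was found? | Used in scoring? |
|---|---|---|---|
| Dye type and volume, microcoils, fiducials, other markers | Synopsis, 4.3.1, 9.9 | No: what was placed | No |
| Resection type and technique; planned and eventual surgery | Synopsis, 4.3.5, 9 | No | Type and technique no; a change of plan only through the 9.2 crossover rules |
| Localization time, total surgical duration | 4.3.2 | No | No |
| Excised weight | 4.3.4 | No | No |
| Margin and pathology | 4.3.4, 9.2 | No | Yes: decides the endpoint |
| Procedures assisting surgical management | 9 | Possibly an added aid; the examples are resection types | No |
| Localization outcomes | 9 | Not specified | No |

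**Step 2. Apply the rule to one case.** The dye is placed but cannot be seen at resection. The surgeon feels the nodule and wedges it out in the first specimen with clear margins. Under section 9.2 this is a successful localization. It involves no crossover and no second specimen, so settling the crossover rules in 9.2 would not change it.

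**Step 3. Size.** Let p be the share of evaluable subjects in whom the mark guided the first resection, and r the share of mark failures in which the nodule was found another way and still removed in the first specimen with clear margins. Assume that every mark-guided resection reaches clear margins. Then:

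- scored rate = p + r(1 − p)
- overstatement = r(1 − p)

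Neither p nor r is in the documents. Scored rates over a range of assumed values:

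| p | r = 25% | r = 50% | r = 75% |
|---|---|---|---|
| 70% | 77.5% | 85% | 92.5% |
| 80% | 85% | 90% | 95% |
| 90% | 92.5% | 95% | 97.5% |

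At p = 80% the overstatement is 0.25 × 0.20 = 5 points or 0.50 × 0.20 = 10 points. At r = 100% every row scores 100%.

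**Step 4. Compare with sampling error.** The planned size is 70 to 100 evaluable subjects (11.1). Exact 95% intervals for p = 80%:

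- r = 50%: 63/70 gives 80.5% to 95.9%; 90/100 gives 82.4% to 95.1%. Both exclude 80%.
- r = 25%: 60/70 (59.5 rounded up) gives 75.3% to 92.9%; 85/100 gives 76.5% to 91.4%. Both include 80%.

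**Step 5. Effect on comparing techniques.** With a common r, the scored difference between two techniques is (1 − r)(p₁ − p₂). For p₁ = 90% and p₂ = 70%, the true difference of 20 points becomes 10 at r = 50% (95% against 85%) and 5 at r = 75% (97.5% against 92.5%).

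**The case against.** Several points on the other side are sound.

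- A reader might infer from section 9.9 that data capture ends before the resection. It does not. That sentence closes the localization part of the operation, and resection, specimen, pathology and safety data follow. The gap is one missing kind of information, together with a scoring rule that would not use it.
- A reader might say that rescue goes wholly unrecorded. That is too strong. Added markers are recorded, so a case with dye plus a second marker can be identified, though order and reason are not specified. A second marker placed percutaneously under navigation is part of the registry technique and not clearly a rescue. Section 9 mentions localization outcomes without saying what they are, and the content of Appendix B is not shown.
- The synopsis restricts the population to subjects in whom the surgeon judges localization warranted, and inclusion requires a decision to use SPiN. This narrows the scope for easily felt nodules. It sets no visibility or palpability standard and asks for no record of one.
- Nodule size, pleural distance and morphology are recorded, and summaries by nodule size are foreseen. These help to locate the problem but do not show which individual marks worked.
- The definition does require successful localization as well as removal. The following sentence, however, lets clear margins stand for it, and pathology is named as decisive.
- The registry is descriptive, with no hypothesis or threshold, and any size rests on assumed p and r. This stands: no particular inflation can be claimed.

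**Conclusion.** The point holds as a gap in attribution. Followed as written, the plan counts a first-specimen, clear-margin wedge as a SPiN localization success however the nodule was found, and no described item lets an analyst separate the mark-guided cases. The headline remains a valid rate of first-specimen clear-margin removal after attempted localization. It is not, on its own, a rate of accurate SPiN localization.

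The size is r(1 − p), with both quantities assumed: 5 to 10 points at p = 80% and r = 25% to 50%. At the upper end the reported interval would exclude the mark-guided rate; at the lower end it would not. The effect may be material but is not shown to be. The conclusion is also conditional on no suitable field existing in the data-element list that is not shown. Such a field would close the recording gap but not the scoring gap. No change in sample size follows.

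**What to change.** Keep the headline rate and its scoring unchanged, and make three additions.

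1. **At first resection, completed before the specimen's pathology is known:** (a) mark identified at resection, yes or no; (b) nodule found for the first resection by the SPiN-placed mark alone / mark plus palpation or vision / palpation or vision without the mark / additional marker or aid after mark failure. State that markers placed before the final needle withdrawal belong to the SPiN-placed mark, so that planned combinations are not coded as rescue.
2. **Before surgery:** whether the surgeon expects the nodule to be visible or palpable if unmarked.
3. **In the analysis:** beside the headline, with the same denominator and a 95% confidence interval, report the rate of first-specimen clear-margin removal guided by the SPiN-placed mark without rescue, overall and in nodules not expected to be visible or palpable. Count the first two categories of (b) as mark-guided, and tabulate all four so that the role of palpation can be seen.

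If the full data-element list already holds an equivalent field, only the third step is needed, plus any missing response options. For a subject operated on before the item is in place, report it as missing under section 11.2.2; reconstruction from charts may be incomplete.

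The cost is three short eCRF entries, the added rate with its one subgroup, a small table, and a protocol amendment. No procedure, visit or subject is added. The drawbacks are that the entries are unblinded surgeon reports and that the mark-guided rate will be equal to or lower than the headline.
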